The generalizability of the treatment effect across geographical area will be tested and the statistical strategy will be defined in the SAP once the sample size will be known by stratum and country and before the break of the randomization code.

There is no planned interim analysis for success. However, the DSMB may decide to perform some futility analyses in particular in case of safety concerns.

A series of sensitivity analyses will be performed to assess the robustness of results such as the use of a stratified test (country as a stratification factor), the use of other sets of patients (PP set, Evaluable set, Randomized set, completer set). In case of missing assessment at W24, the patient will be considered a non-responder. A responder is consequently a confirmed responder.

Secondary efficacy analyses:

- NASH improver rates in each dose will be compared to placebo using the Cochran Mantel Haenszel test stratified on diabetes.
- Percent of patients with resolution of NASH in each dose will be compared to placebo using the Cochran Mantel Haenszel test stratified on diabetes.
- Percent of patients with a change in components of SAF score in each dose will be compared to placebo using the Cochran Mantel Haenszel test stratified on diabetes.
- Percent of patients with at least 1-point improvement of fibrosis without worsening of NASH in each dose will be compared to placebo using the Cochran Mantel Haenszel test stratified on diabetes.

Planned exploratory analyses:

- Inflammatory markers (fibrinogen, hs-CRP, alpha2 macroglobulin and haptoglobin levels) change from baseline to end of treatment (week 24) will be compared using GLM with the diabetes and dose as covariates. A mixed model for repeated measures will also be used to compare the time course of the response of each treatment group.
- Transient Elastography and Controlled Attenuation Parameter change from baseline to end of treatment (week 24) will only be described.
- Glucose metabolism (fasting glucose and insulin, HOMA index and, in subjects with T2DM, HbA1c) change from baseline to end of treatment (week 24) will be compared using GLM with the diabetes

and dose as covariates. A mixed model for repeated measures will also be used to compare the time course of the response of each treatment group.

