- an Analysis of Covariance (**ANCOVA**) using the SAS MIXED procedure with the treatment and the diabetic status as covariates when specified

Or

- a Mixed Model for Repeated Measures (**MMRM**) when specified using the SAS MIXED procedure with:
  - a. The absolute change from baseline of the analysis variable as endpoint (MODEL statement of the MIXED procedure)
  - b. The time, treatment, the diabetic status, the interaction (treatment \* time) and the baseline value as fixed effects (MODEL statement of the MIXED procedure). Time, treatment and diabetic status being considered as categorical variables
  - c. A time repeated measure (REPEATED statement of the MIXED procedure) within each subject (SUBJECT = subject as option of the REPEATED

statement). An unstructured (type=UN) variance covariance matrix being used as option of the REPEATED statement

- d. The Kenward-Roger approximation to estimate denominator degrees of freedom and adjust standard errors (ddfm=kr option in MODEL statement)

In order to explore the validity of the model (and more accurately the assumption regarding independence, normality and constant variance of residuals), the following graphs will be provided: Q-Q plot of the residuals, distribution of residuals with its corresponding normal density estimate and scatterplot of residuals vs. predicted values.

With such models (ANCOVA, MMRM) different treatment effects will be evaluated:

- **Evaluation of treatment effect (Each dose vs. placebo) at week 24:** In order to evaluate each treatment dose versus placebo at week 24 the following contrasts of interest will be used:
  - o 800 mg/day vs. placebo: -1 for Placebo, 1 for 800 mg/day and 0 for 1200 mg/day
  - o 1200 mg/day vs. placebo: -1 for Placebo, 0 for 800 mg/day and 1 for 1200 mg/day.

In order to take into account multiplicity of tests, the ascending Hochberg procedure will be applied (see section 4.1.5).

- **Evaluation of dose effect (800 mg vs. 1200 mg) at week 24:** In order to evaluate the dose of 800 mg/day versus the dose of 1200 mg/day at week 24 the following contrast of interest will be used:
  - o 800 mg/day vs. 1200 mg/day: 0 for Placebo, -1 for 800 mg/day and 1 for 1200 mg/day
- **Time course of the response of each treatment group:** In order to evaluate the time course of the response of each dose (separately) at each time-point the following contrasts of interest will be used for each dose:

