  - o week 4 vs. week 14: -1 for week 4, 1 for week 14, 0 for week 24 and 0 for week 28
  - o week 4 vs. week 24: -1 for week 4, 0 for week 14, 1 for week 24 and 0 for week 28
  - o week 4 vs. week 28: -1 for week 4, 0 for week 14, 0 for week 24 and 1 for week 28
  - o week 14 vs. week 24: 0 for week 4, -1 for week 14, 1 for week 24 and 0 for week 28
  - o week 14 vs. week 28: 0 for week 4, -1 for week 14, 0 for week 24 and 1 for week 28
  - o week 24 vs. week 28: 0 for week 4, 0 for week 14, -1 for week 24 and 1 for week 28

In order to take into account multiplicity of tests, the ascending Hochberg procedure will be applied (see section 4.1.5).

Lowest dose will always be considered as reference for treatment effect calculation. As well as earliest visit will always be considered as reference for time course evaluation.

Comparisons of treatment groups for **qualitative variables** will be done using the FREQ procedure with Cochran–Mantel–Haenszel (CMH) test option, stratified on the diabetic status at Baseline (yes/no). The primary measure of the effect size will be the CMH odds ratio with an adjustment for diabetic status. Because the odds ratio is not easy to interpret when the rate of responders in the placebo group is not very small the odds ratio (OR) will be converted in

Risk Ratio (RR) using the following formula  $RR = (P1/P0) = OR/[(1-P0) + (P0 \times OR)]$ . The same formula will be applied to OR 95% CI lower and upper bounds to obtain RR 95% CI. The log-binomial model will preferentially be used in the absence of convergence or estimability issue for estimating the effect size with RR. The primary handling of heterogeneity of result across strata will be performed through the Breslow-Day test. If the homogeneity hypothesis is rejected, then the estimate of the difference in percentage points between each dose and placebo along with the 95% C.I. will be provided within each stratum, as well as the p-value of the association test between treatment and qualitative variable (Chi-2 test or Fisher's exact test). If the interaction between stratum and treatment (Breslow Day test) is significant it means that the treatment effect has not the same magnitude in diabetic and non-diabetic patients. In the absence of qualitative interaction there will be no further adjustment of the type one error for multiplicity of testing. Smallest dose will always be considered as reference for OR/RR calculation.

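### The SAP's time-course tests compare visits within each dose; no dose-versus-placebo contrast is specified at weeks 4, 14 or 28

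*SAP*

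**What the plan says.** Protocol 9.7.4, among the planned exploratory analyses, states for inflammatory markers, glucose metabolism, plasma lipids and adiponectin: "A mixed model for repeated measures will also be used to compare the time course of the response of each treatment group".

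SAP 4.1.5 specifies the mixed model. Its response is "The absolute change from baseline of the analysis variable as endpoint", and its fixed effects are "The time, treatment, the diabetic status, the interaction" of treatment with time, and the baseline value. Three sets of contrasts follow:

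- Each dose against placebo, at one visit: "In order to evaluate each treatment dose versus placebo at week 24 the following contrasts of interest will be used".
- 800 mg against 1200 mg, also at week 24.
- The time course, introduced by "In order to evaluate the time course of the response of each dose (separately) at each time-point". Six contrasts cover all pairs of weeks 4, 14, 24 and 28, for example "week 4 vs. week 24: -1 for week 4, 0 for week 14, 1 for week 24 and 0 for week 28". The reference is a visit, not an arm: "As well as earliest visit will always be considered as reference for time course evaluation".

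The time-course tests are adjusted: "In order to take into account multiplicity of tests, the ascending Hochberg procedure will be applied (see section 4.1.5"). SAP 5.2.3.8 to 5.2.3.10 apply them to fasting glucose and HbA1c, to ALT, AST and GGT, and to total cholesterol, HDL-C, LDL-C and triglycerides. The SAP lists no test of the treatment-by-time interaction. SAP 4.6.4, which records changes to the efficacy analysis, does not mention the time course.

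**The concern.** The SAP introduces all three sets of contrasts as evaluations of treatment effects. The third set is not one. It asks whether the mean in one arm moved between two visits, and any movement shared with placebo counts towards the answer.

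The intermediate and follow-up visits can show how soon an effect appears against placebo and how much of it remains four weeks after treatment stops. The planned p-values answer neither question. With six contrasts, two doses and nine variables there are 6 × 2 × 9 = 108 of them (162 if placebo is tested too, which the reference to each dose leaves unclear). If placebo is tested, a significant result in one arm and a non-significant one in another is still not a test of the difference between them.

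**Working it through.** **1. What each contrast estimates.** Write the mean change from baseline in arm *a* at visit *t* as drift(*t*) + effect(*a*,*t*), with effect zero for placebo.

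- SAP time-course contrast, visit *s* to *t* in one dose: [drift(*t*) − drift(*s*)] + [effect(*t*) − effect(*s*)].
- Dose minus placebo at visit *t*: effect(*t*). Drift cancels.
- Dose minus placebo in the change from *s* to *t*: effect(*t*) − effect(*s*). Drift cancels.

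The within-arm contrast can therefore be non-zero with no drug effect. It can also be zero with a real one: an effect complete by week 4 and then constant drops out of every on-treatment pair.

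**2. Inputs for an illustration.** The documents attach no figure to this analysis, so there is none to reproduce.

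- From the documents: 75 per arm (Protocol 9.2), two-sided 5% and critical values (*i*/*m*)*Q* (SAP 4.1.5).
- Assumed: correlation 0.6 between visits; the same drift in every arm, steady from week 4 to week 24 and flat to week 28; no drug effect; complete data; the six contrasts in one arm as the multiplicity family. SAP 5.2.3.8 speaks of adjusting at each time point, so the intended family is not certain.

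**3. One contrast, unadjusted.** SE = √(2 × (1 − 0.6)/75) = 0.103 SD.

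- Week 4 to week 24, drift 0.2 SD: 0.2/0.103 = 1.94, rejection about 49%.
- Week 4 to week 24, drift 0.3 SD: 0.3/0.103 = 2.90, rejection about 83%.
- Week 4 to 14, or 14 to 24, carries half the drift: 0.10/0.103 = 0.97 gives about 16%, and 0.15/0.103 = 1.45 gives about 31%.
- Week 24 to 28 carries none: 5%.

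The 247 actually randomised (SAP 3.5) are about 82 per arm. That would raise the first two figures to about 53% and 86%.

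**4. Six contrasts under the SAP's rule (simulation, no drug effect).**

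| Common drift, week 4 to 24 | At least one of six, given arm | Week 4 v 24 or 28 | Week 4 v 14, 14 v 24, 14 v 28 | Week 24 v 28 | Dose v placebo, one contrast |
|---|---|---|---|---|---|
| 0 | 4–5% | 1% | 1% | 1% | 5% |
| 0.1 SD | 11–12% | 6% | 2–3% | 1–2% | 5% |
| 0.2 SD | 40–41% | 27–29% | 8% | 2% | 5% |
| 0.3 SD | 78–79% | 66–68% | 20–22% | 3% | 5% |

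Step-up critical values of α/(*m* − *i* + 1) in place of (*i*/*m*)*Q* give 39% and 77% for at least one of six at 0.2 and 0.3 SD, so the choice of multiplicity rule is not what drives the result.

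**5. Where the protocol and SAP conflict.** The protocol sentence covers glucose metabolism and lipids, so it reaches six of the nine variables: fasting glucose, HbA1c and the four lipids. It does not name the liver enzymes. The inflammatory markers, insulin, apoA1 and adiponectin are measured only at baseline and week 24, so they have no time course to compare.

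**The case against.** The case on the other side has real weight.

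- *Descriptive between-arm information is planned.* SAP 5.2.3.8 gives values and changes from baseline by treatment group, placebo included, with 95% CIs of the means and a graph over time. The sections on enzymes and lipids use the same method. This stands. A reader might infer that onset and offset cannot be attributed to the drug at all, but concurrent randomised placebo data are shown at every visit. What is missing is a formal estimate of the difference, with its interval.
- *The SAP draws no efficacy conclusion from these contrasts.* It says each dose is taken separately, which fits a description of plateau or reversal. This stands as far as it goes, but description needs no adjusted p-values, and the section presents them among treatment effects.
- *The SAP prevails.* Protocol 9.7.4 lets SAP clarifications override other readings unless they cause major inconsistencies, and its sentence names no contrast or visit. Yet replacing a comparison of groups by separate tests within groups changes the question, and SAP 4.6 does not record it.
- *Multiplicity is controlled.* Adjustment limits chance findings when the mean does not move. It offers no protection when the mean moves in every arm.
- *The drift is assumed.* Correct. Nothing in the documents gives its size, and with no drift the error rate is nominal.

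Two further inferences should be avoided. The unadjusted 49 to 83% does not apply to each of the six contrasts: it is the week 4 to 24 figure, and a steady drift cannot be equally large between every pair of visits. Regression to the mean is also a weak explanation, because all six contrasts lie between post-baseline visits and the model adjusts for baseline.

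**Conclusion.** The point holds in a limited form. For nine laboratory variables the planned time-course p-values test movement within an arm, not a drug effect, and no dose-versus-placebo estimate is specified at weeks 4, 14 or 28. For six of the nine this also departs, without being recorded, from the natural reading of the protocol.

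The size depends on common drift, which is an assumption. At 0.2 to 0.3 SD with 75 per arm and correlation 0.6, a given arm shows at least one significant contrast in about 40 to 79% of trials with no drug effect; with no drift this is about 4 to 5%. The qualitative conclusion follows from the contrast coefficients alone.

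A reader might take this as a weakness in the efficacy evidence. It is not: the stratified primary test, the histology endpoints and the week-24 dose-versus-placebo contrasts are all between-arm. This is a worthwhile improvement to a supporting analysis, and no trial decision rests on it.

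**What to change.** In SAP 4.1.5, using the mixed model already specified:

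1. Add dose-minus-placebo contrasts, for each dose, with 95% CIs at weeks 4, 14 and 28, and make these the time-course result alongside week 24.
2. For offset, add the dose-minus-placebo difference in the week 24-to-28 change, and label week 28 as off treatment.
3. Keep the six within-arm contrasts as estimates with CIs and no p-values, and produce them for placebo as well.
4. State whether the added contrasts are adjusted for the two doses or reported at nominal level.
5. Record the change in SAP 4.6.4.

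The cost is a few contrast statements in a model that will be fitted anyway. No new data, no new model and no change to the primary analysis are needed. The change should be made before database lock and release of the randomization codes.

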#### 9.7.4 *Efficacy Analyses*

##### Primary efficacy analysis

The primary population will be the intent to treat FAS population composed of all randomized subject who received at least one dose.

The primary efficacy endpoint will be a binary variable (responder / non responder) based on the change from baseline to Week 24 of the SAF activity score. Responder is defined as a decrease from baseline to week 24 of at least 2 points of the SAF activity score combining hepatocellular inflammatory and ballooning without worsening of fibrosis.

The primary tests of hypotheses will be the Cochran Mantel Haenszel test stratified on diabetes comparing the high dose to placebo and the low dose to placebo. The ascending Hochberg procedure will be used for adjusting the type one error which is globally set at 0.05 two-sided. The primary measure of the effect size will be the CMH odds ratio with an adjustment for diabetes. Because the odds ratio is not easy to interpret when the rate of responders in the placebo group is not very small the odds ratio (OR) and its confidence interval will be converted in Risk Ratio (RR) using the following formula  $RR = (P_1/P_0) = OR / [(1-P_0) + (P_0 \times OR)]$  (75). The log-binomial model will preferentially be used in the absence of convergence or estimability issue for estimating the effect size with RR.

The primary rule for handling the missing data is to consider non-responders all patients who are not confirmed responders.

The primary handling of centers is to ignore in the primary analysis the center effect because 30+ centers should be involved in the study and the number of empty cells in the breakdown of the site by treatment by stratum table can be large (sparse contingency table).

The primary handling of multiplicity of testing will be done through the Hochberg procedure.

The primary handling of heterogeneity of result across strata will be performed through the Breslow-Day test. If the homogeneity hypothesis is rejected, then the estimate of the difference in percentage points between each dose and placebo along with the 95% C.I. will be calculated within each stratum. If the interaction between stratum and treatment (Breslow Day test) is significant it means that the treatment effect has not the same magnitude in diabetic and non-diabetic patients. In the absence of qualitative interaction there will be no further adjustment of the type one error for multiplicity of testing.

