## 4.2 Sample size calculation

The expected rate of responders according to the retained definition was estimated to 10% for the placebo by a group of clinical experts. An excess rate of responders of 20% was accepted as clinically pertinent. It corresponds to a multiplication of chance of success (responders) of 3 and a NNT (Number Needed to Treat) of 5. The sample size required to reach a power of at least 80% is 72 patients per group with a two-sided alpha of 0.025 (adjustment for multiplicity). The sample size is sensitive to the rate of responders in the placebo group. For example, if the rate of responders is 15% instead of 10% then 85 patients are required. If the true rate is lower than 10% then less patients may be sufficient. The sample size is therefore rounded in the conservative side of 75 patients per group.

Based on the experience of previous clinical trials, it is estimated that 100 patients per group will need to be screened to randomise 75 patients after central reading of liver biopsy confirms the NASH diagnosis and activity (screening failure rate of 25%). However, as detailed in section 3.5, the observed screening failure rate was of 72%), consistent with all other clinical trial performed in NASH with such a high screening failure rate.

In case the end of study liver biopsy slides are not available or not interpretable in more than 5% of patients, an amendment will be submitted to increase sample size accordingly.

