#### **Evaluation of treatment effect (each dose versus placebo)**

Each treatment dose will be compared to placebo using a CMH test stratified on the diabetic status.

In order to take into account multiplicity of tests, the ascending Hochberg procedure will be applied (see section 4.1.5 for details). The p-values of the 2 tests will be provided and will provide conclusions regarding the primary objective of the study met or not met.

Corresponding CMH Odds ratio (OR) and adjusted-Relative Risk (RR) will be provided with their 95% confidence intervals, in the FAS for the two lanifibranor groups.

The Breslow-Day test will be implemented for homogeneity of the odds ratios between diabetic and non-diabetic patients:

- If the test is significant, then this means that the treatment effect has not the same magnitude in diabetic and non-diabetic patients (significant difference in OR in the 2 populations)
- If the test is not significant, then this means that the treatment effect has the same magnitude in diabetic and non-diabetic patients (no significant difference in OR in the 2 populations).
- Regardless the significance of the test, both OR and RR in diabetic and non-diabetic patients will be provided with their 95% confidence interval

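### Where the risk ratio is taken from the converted odds ratio (best read as the fallback to the log-binomial model), its 95% interval is too narrow: about 90% coverage at the design rates

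*SAP*

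**What the plan says.** SAP 4.1.5, in the part on qualitative variables, makes the CMH odds ratio adjusted for diabetes the primary effect measure. It adds a risk ratio for ease of interpretation, obtained from the odds ratio by the formula above. For the limits it says: "The same formula will be applied to OR 95% CI lower and upper bounds to obtain RR 95% CI". Protocol 9.7.4 agrees: "the odds ratio (OR) and its confidence interval will be converted in Risk Ratio (RR) using the following formula".

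In both documents a later sentence gives preference to a log-binomial model for the risk ratio, provided there is no convergence or estimability problem. That sentence concerns estimation of the effect size and does not mention limits.

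SAP 5.2.2.1 then promises the result for the primary endpoint without naming a method: "Corresponding CMH Odds ratio (OR) and adjusted-Relative Risk (RR) will be provided with their 95% confidence intervals". It also asks for odds ratios and risk ratios with intervals within the diabetic and non-diabetic strata, whatever the Breslow-Day result. SAP 5.2.3 carries the same methodology to the other binary histology endpoints.

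**The concern.** The conversion needs P0. Putting only the odds-ratio limits through it carries the uncertainty of the odds ratio but leaves out the sampling error of P0, and its correlation with the odds ratio. When the drug works, the resulting limits are too close together.

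What is at stake is the stated precision of the risk ratio for the primary endpoint and for each binary histology endpoint that borrows the method. A fallback is most likely to be triggered where models are fragile, such as rare composite endpoints or a single diabetes stratum, and it has to be valid there. Because SAP 5.2.2.1 names no method, a programmer could also produce the converted interval as the main one and still be following the text.

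**Working it through.** **Inputs.** SAP 4.2 gives the design rates: "The expected rate of responders according to the retained definition was estimated to 10% for the placebo by a group of clinical experts" and "An excess rate of responders of 20% was accepted as clinically pertinent", so 10% v 30%. It also gives an alternative: "if the rate of responders is 15% instead of 10% then 85 patients are required", so 15% v 35%. The plan was 75 per arm. SAP 3.5 reports 247 randomised, and 247/3 is about 82 per arm. The documents give no diabetes split and do not say whether P0 is crude or stratum-weighted. I assume two equal strata and the crude observed placebo rate. The pairs 30% v 50%, 40% v 60%, 10% v 20% and 10% v 40% are assumptions, used to show the range.

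**The plan's own figures.** With n = [P0(1−P0)+P1(1−P1)] × (z₀.₉₈₇₅+z₀.₈₀)²/d² and (2.2414+0.8416)² = 9.505:
- 10% v 30%: 0.30 × 9.505/0.04 = 71.29, so 72.
- 15% v 35%: 0.355 × 9.505/0.04 = 84.36, so 85.

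Both match SAP 4.2, so the rates are read as intended. The documents state no coverage for the risk-ratio interval, so there is nothing further to reproduce.

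**Large-sample check.** With P0 fixed, the slope of log RR on log OR is (1−P0)/[(1−P0)+P0×OR] = 1−P1. The converted interval therefore uses SE = (1−P1) × SE(log OR). The correct value is SE(log RR) = √[(1−P0)/(nP0) + (1−P1)/(nP1)].

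At 10% v 30% and n = 75:
- SE(log OR) = √[1/(75×0.09) + 1/(75×0.21)] = 0.460
- converted SE = 0.70 × 0.460 = 0.322
- correct SE = √(0.120+0.0311) = 0.389
- ratio 0.83, so coverage = 2Φ(1.96×0.828)−1 = 89.6%

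With equal arms the ratio does not depend on n. At no effect it is exactly 1.

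**Simulation.** 82 per arm, two equal strata, 200,000 trials per scenario. The Mantel-Haenszel odds ratio and its 95% limits were converted with the observed placebo rate.

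| Placebo v active | SE ratio (formula) | Coverage (formula) | Coverage (simulated) |
|---|---|---|---|
| 10% v 30% | 0.83 | 89.6% | 90.3% |
| 15% v 35% | 0.83 | 89.6% | 89.9% |
| 30% v 50% (assumed) | 0.81 | 88.8% | 88.5% |
| 40% v 60% (assumed) | 0.78 | 87.6% | 87.1% |
| 10% v 20% (assumed) | 0.92 | 93.0% | 93.8% |
| No effect, 10% | 1.00 | 95.0% | 96.1% |

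In the first four rows the simulated converted interval is 18 to 21% too narrow on the log scale, while the Mantel-Haenszel risk-ratio interval covers 95.1 to 96.0%. At 10% v 30%, 6.3% of converted intervals lie wholly below the true risk ratio and 3.4% wholly above. A separate run at 75 per arm gave 90.1%, 89.9% and 88.5% for the first three rows, and 84.5% for a larger effect, 10% v 40%.

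**The preferred method.** A log-binomial model adjusted for diabetes, 75 per arm and 1,500 trials per scenario, covered 96.3% (10% v 30%), 96.5% (15% v 35%) and 94.5% (30% v 50%). It gave a usable fit in every trial.

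**One data set.** Take 8/75 v 22/75, unstratified:
- OR = (22×67)/(53×8) = 3.48, with limits 1.43 to 8.43.
- Converted with P0 = 0.107: RR 2.75 (1.37 to 4.70).
- Direct, with SE = √(1/22−1/75+1/8−1/75) = 0.379: RR 2.75 (1.31 to 5.78).

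**The case against.** The strongest reply is that the plan does not intend to report this interval. The log-binomial model is given preference, with a condition for departing from it, and at the simulated rates it fitted every time with near-nominal coverage. That largely stands. A reader might infer that the published risk ratio will carry the faulty limits, or that the SAP sets two rules on an equal footing. The order of preference supports neither reading. The silence of SAP 5.2.2.1 does not promote the lower-ranked method.

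It is also fair to say that little depends on the risk ratio. The odds ratio is the primary measure, and success rests on the CMH p-values with Hochberg. The conversion is monotone and maps 1 to 1, so a converted interval excludes 1 exactly when the odds-ratio interval does. Responder percentages have their own exact intervals. All of this stands, and it rules out any inference that the trial's conclusion or its type I error is at risk.

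Finally, the lowest coverage figures rest on placebo rates of 30% and 40%, or on a large effect, none of which is in the documents. At the documented rates the figure is about 90%.

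Two things survive. The conversion is written as an unconditional instruction and is the only one that mentions risk-ratio limits. A named fallback also has to be valid when it is used, and this one is not.

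**Conclusion.** The conversion rule for the limits is wrong as written, and the consequence is confined to cases where the conversion is used. There, a nominal 95% interval covers about 90% at the plan's design rates, so it misses about 10% of the time where 5% is claimed. It covers about 87 to 88% at the higher assumed rates. The shortfall shrinks to about one point at 10% v 20% and disappears at no effect. The problem therefore appears when the drug works, which is also when the risk ratio is of most interest.

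These figures assume the crude placebo rate for P0 and equal diabetes strata. Other settings examined (75 per arm, no strata) were within about a point. With unequal stratum rates and a common odds ratio, coverage was 88.3 to 91.9%.

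This is a matter of reported precision for a supporting effect measure. The primary test, the multiplicity procedure and the CMH odds ratio are sound on this point.

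**What to change.** In SAP 4.1.5 and 5.2.2.1:
- State that the reported risk ratio and its 95% interval both come from the log-binomial model adjusted for diabetes.
- Delete the odds-ratio-to-risk-ratio conversion, for the estimate as well as the limits, so that estimate and interval always share a method.
- Name the Mantel-Haenszel common risk ratio stratified on diabetes, with its own 95% interval, as the fallback if the model does not converge or is not estimable. It comes from the FREQ/CMH run already planned.
- For the within-stratum risk ratios in 5.2.2.1, name a direct risk ratio with its own interval in the same way.

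Keep the CMH odds ratio as the primary measure. Protocol 9.7.4 allows the SAP to clarify the analysis, so the change can be made there and listed in SAP 4.6 as a modification. The cost is a few sentences and, when the fallback is used, somewhat wider risk-ratio intervals, as in the example above (1.31 to 5.78 in place of 1.37 to 4.70).
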